9.2.2. Suspected Unexpected Serious Adverse Reactions

Suspected unexpected serious adverse reactions (SUSARs) are serious events that are not listed in the IB and that the investigator identifies as related to study treatment or study procedure. United States 21 CFR 312.32 and European Union Clinical Trial Directive 2001/20/EC and the associated detailed guidances or national regulatory requirements in participating countries require the reporting of SUSARs. Lilly has procedures that will be followed for the recording and expedited reporting of SUSARs that are consistent with global regulations and associated detailed guidances.

9.2.3. Complaint Handling

Lilly collects product complaints on investigational products and drug delivery systems used in clinical studies in order to ensure the safety of study participants, monitor quality, and to facilitate process and product improvements.

Patients should be instructed to contact the investigator as soon as possible if he or she has a complaint or problem with the investigational product so that the situation can be assessed.

9.3. Treatment of Overdose

Refer to the IB for the current guidance on overdose.

9.4. Safety

9.4.1. Other Safety Measures

For each patient, safety assessments, including ECGs, vital signs, and laboratory tests, should be collected as shown in the Schedule of Activities (Section 2). ECGs should be recorded according to the study-specific recommendations that will be provided separately.

As of 27 August 2015, no patients treated with LY2606368 monotherapy have had an average QTcF interval >480 msec at any time point. However, if a patient experiences a QTcF interval >480 msec, the patient should be monitored for signs of life-threatening arrhythmias such as torsades de pointes. It should be confirmed that the measurement is correct by repeating the ECG and ruling out other causes such as atrial fibrillation or the presence of a pacemaker. If the result is confirmed, institutional guidelines or standard of care measures for management of QTcF interval >480 msec and/or associated arrhythmias should be initiated. These actions may include the administration of IV magnesium sulfate and the assessment of clinical chemistry. If electrolytes are abnormal, they should be repeated as indicated. The QTcF value should be monitored until the interval has returned to <480 msec or at least to predose levels. It is recommended that the patient be assessed by a cardiologist before leaving the treating facility. For all subsequent doses, an ECG must be obtained at 10 minutes after the end of infusion (EOI) (± 5 minutes), 30 minutes after EOI (± 10 minutes), and >1 hour after EOI.

If a patient experiences a QTcF interval >500 msec and has an associated life-threatening arrhythmia, he/she should be discontinued from study treatment. If a patient experiences a QTcF interval >500 msec without an associated life-threatening arrhythmia and if the investigator deems it in the best interest of the patient, the patient may continue treatment with LY2606368. If a patient has a second occurrence of QTcF interval >500 msec, he/she should be discontinued from study treatment.

Any clinically significant findings that result in a diagnosis and that occur after the patient receives the first dose of LY2606368 should be reported to Lilly or its designee as an AE via CRF/electronic data entry/designated data transmission methods.

9.4.2. Safety Monitoring

Lilly will periodically review evolving aggregate safety data within the study by appropriate methods.

Details for hepatic monitoring depend upon the severity and persistence of observed laboratory test abnormalities. To ensure patient safety and comply with regulatory guidance, the investigator is to consult with the Lilly CRP regarding collection of specific recommended clinical information and follow-up laboratory tests. See [Appendix 5](#).

- If a patient experiences elevated alanine aminotransferase (ALT) $\geq 5 \times$ upper limit of normal (ULN) and elevated total bilirubin $\geq 2 \times$ ULN, clinical and laboratory monitoring should be initiated by the investigator.
- For patients entering the study with ALT $\geq 3X$ ULN, monitoring should be triggered at ALT $\geq 2X$ baseline and elevated total bilirubin $\geq 2 \times$ ULN.

9.5. Pharmacokinetics

Pharmacokinetic samples will be collected as specified in the Pharmacokinetic Sampling Schedule ([Appendix 4](#)).

At the visits and times specified in the Study Schedule, venous blood samples will be collected to determine the plasma concentrations of LY2606368. A maximum of 5 samples may be added or removed during the study if warranted and agreed upon between both the investigator and Lilly. Instructions for the collection and handling of blood samples will be provided by the sponsor. The actual date and time (24-hour clock time) of each sampling will be recorded.

These samples will be analyzed at a laboratory designated by the sponsor by using a validated liquid chromatography–mass spectrometry/mass spectrometry (LC-MS/MS) method.

The PK samples will be stored at a facility designated by the sponsor. Bioanalytical samples collected to measure LY2606368 concentrations will be retained for a maximum of 1 year following last patient visit for the study.

9.6. Pharmacodynamics

Pharmacodynamics samples will not be collected for this trial.

9.7. Pharmacogenomics

9.7.1. Whole Blood Sample for Pharmacogenetic Research

A whole blood sample will be collected for pharmacogenetic analysis as specified in [Section 2](#), where local regulations allow.

Samples will not be used to conduct unspecified disease or population genetic research either now or in the future. Samples will be used to investigate variable response to LY2606368 and to investigate genetic variants thought to play a role in SCLC. Assessment of variable response may include evaluation of AEs or differences in efficacy.

All samples will be coded with the patient number. These samples and any data generated can be linked back to the patient only by the study site personnel. Samples will be retained for a maximum of 15 years after the last patient visit for the study, or for a shorter period if local regulations and/or ethical review boards (ERBs)/institutional review boards (IRBs) impose shorter time limits, at a facility selected by Lilly or its designee. This retention period enables use of new technologies, response to questions from regulatory agencies, and investigation of variable response that may not be observed until later in the development of LY2606368 or after LY2606368 becomes commercially available.

Molecular technologies are expected to improve during the 15-year storage period and therefore cannot be specifically named. However, existing technologies include whole genome and exome sequencing, genome-wide association studies, multiplex assays, candidate gene studies, and epigenetic analyses. Regardless of the technology utilized, data generated will be used only for the specific research scope described in this section.

9.8. Biomarkers

Biomarker research is performed to address questions of relevance to drug disposition, target engagement, mechanism of action, variability of patient response (including safety), and clinical outcome. Sample collection is incorporated into clinical studies to enable examination of these questions through measurement of biomolecules including DNA, RNA, proteins, lipids, and other cellular elements.

As part of Lilly's ongoing efforts to understand the relationship between cancer, genetics, and response to therapy, this study will analyze biomarkers relevant to the mechanism of action of CHK1, DNA damage response pathways or downstream effects, cell cycle markers, immune function, and cancer pathobiology and/or for related research methods or validation of diagnostic tools or assays.

Samples for biomarker research will be collected as specified in Section 2 where local regulations allow. It is possible that biomarker data for patients in the study have already been generated from samples that were collected and analyzed before the patients' enrollment in this trial. This may include data generated from genetic analyses. If available, these data may be requested from medical records for use in the research described in Sections 9.8.1 and 9.8.2. Samples for biomarker research will be collected as specified Section 2, where local regulations allow.

9.8.1. Blood Samples

Plasma samples for biomarker research will be collected as specified in Section 2 where local regulations allow.

Samples will be examined for biomarkers related to SCLC, variable response to LY2606368, the mechanism of action of LY2606368, and/or for research-related methods or validating diagnostic tools or assays.

All samples will be coded with the patient number. These samples and any data generated can be linked back to the patient only by the study site personnel.

Samples will be retained for a maximum of 15 years after the last patient visit for the study, or for a shorter period if local regulations and/or ERBs/IRBs impose shorter time limits, at a facility selected by Lilly. This retention period enables use of new technologies, response to questions from regulatory agencies, and investigation of variable response that may not be observed until later in the development of LY2606368 or after LY2606368 becomes commercially available.

9.8.2. Tissue Samples

Tumor tissue will be examined for biomarkers related to the mechanism of action of CHK1, DNA damage response pathways or downstream effects, cell cycle markers, immune function, and cancer pathobiology. These markers may also be evaluated to assess any potential correlation with response to LY2606368.

Collection of the following tumor tissue sample(s) **is required** for all patients:

- an archived tumor sample (a block or slides) or a newly obtained biopsy specimen collected prior to treatment with LY2606368, if an archived tumor sample is not available, if not restricted by local regulations
- for patients who do not have archived tissue available and who have disease in technically challenging sites to obtain a fresh biopsy, the investigator and sponsor may agree to enroll the patient without tumor tissue. The joint decision must be documented in writing before the patient receives the first dose of LY2606368 and will not constitute a protocol violation.

Collection of the following tumor tissue sample(s) is **optional** for all patients:

- patients that have archived tumor tissue to meet the inclusion criteria for Study JTJH may also have an optional pre-treatment biopsy
- following treatment with LY2606368, patients may be asked to undergo collection of additional optional on-study, post-treatment, and/or post-progression biopsies for biomarker research from patients willing to consent. In particular, biopsies from lesions in patients who have received clinical benefit and subsequently progress may help identify molecular features that may explain treatment response and resistance mechanisms. Post-progression biopsies should be performed prior to the start of subsequent cancer treatment. However, the procedure should not impede or delay the planned cancer treatment.

Formalin-fixed paraffin-embedded tumor tissue obtained from the primary tumor or metastatic site should be provided as a block or unstained slides. Due diligence should be used to make sure that tumor sample (not a normal adjacent or a tumor margin sample) is provided. Pathology notes/report accompanying archival tissue may also be requested. The notes/report should be coded with the patient number. Personal identifiers, including the patient's name and initials, must be removed from the institutional pathology notes/report prior to submission. Archival

blocks will be sectioned and returned to the study site. Slides and tissue samples collected on-study will not be returned.

Samples will be retained for a maximum of 15 years after the last patient visit for the study, or for a shorter period if local regulations and/or ERBs/IRBs impose shorter time limits, at a facility selected by Lilly or its designee. This retention period enables use of new technologies, response to questions from regulatory agencies, and investigation of variable response that may not be observed until later in the development of LY2606368 or after LY2606368 becomes commercially available.

Technologies are expected to improve during the 15-year storage period and therefore cannot be specifically named. However, existing technologies, including mutation profiling, copy number variability, gene expression, multiplex assays, and/or immunohistochemistry, may be performed on these tissue samples to assess potential associations with these biomarkers and clinical outcomes.

9.9. Health Economics

The primary health outcomes research goal is to evaluate the association between best tumor response and change from baseline in lung cancer-specific symptoms, symptomatic distress, activity status, overall quality of life, total Lung Cancer Symptom Scale (LCSS) score, and Average Symptom Burden Index (ASBI) for patients who have platinum-sensitive or platinum-resistant/refractory SCLC. Patient-reported outcomes and symptoms will be assessed by the LCSS patient scale. The LCSS is a validated tool that has been broadly used in lung cancer research and is available in over 30 different languages.

The LCSS (Hollen et al. 1994) consists of 9 total items, each with a 100-mm line depicting the visual analog scale (VAS). Scores equal the length of line as marked by patient and range from 0 (for best outcome) to 100 (for worst outcome). Six items are symptom-specific measures for lung cancer (appetite loss, fatigue, cough, dyspnea, hemoptysis, and pain) that address 2 dimensions: physical and functional. There are also 3 summation items that describe symptomatic distress, activity status, and overall quality of life.

The LCSS will be administered as shown in the Schedule of Activities (Section 2). The LCSS will be completed by patients when a language translation is available in which the patient is fluent or literate. The recall period is 24 hours and the typical completion time is 8 minutes initially for demonstration of VAS; 3 to 5 minutes for subsequent administrations. To avoid biased responses, the questionnaires should be administered prior to extensive contact with study personnel and clinicians and prior to study drug administration.

10. Statistical Considerations

10.1. Sample Size Determination

The study will enroll approximately 116 patients (58 platinum-sensitive patients, 58 platinum-refractory/resistant patients).

For the platinum-sensitive cohort, it is assumed that a true overall response rate (ORR) of less than 20% indicates inadequate antitumor activity. Given that a futility interim analysis will be conducted on the first 29 patients' response data, then with a one-sided significance level of 0.1, a sample size of 58 patients will provide approximately 90% power to detect a true ORR of at least 35%, i.e. 16 or more confirmed overall responses (complete response [CR] or partial response [PR]) are observed in all 58 patients.

For the platinum-refractory/resistant cohort, it is assumed that a true ORR of less than 5% indicates inadequate anti-tumor activity. Given that a futility interim analysis will be conducted on the first 29 patients' response data, then with a one-sided significance level of 0.1, a sample size of 58 patients will provide approximately 90% power to detect a true ORR of at least 15%, i.e. 6 or more confirmed overall responses (CR or PR) are observed in all 58 patients.

For each cohort, the overall type II error rate, i.e. the probability of terminating an effective cohort, will be controlled using a Lan-DeMets spending function (Lan and DeMets 1983), which generates boundaries that are very similar, though not identical, to the classical stopping boundaries of O'Brien and Fleming (1979). The type II error rate spent at interim analysis after the first 29 patients for each cohort is approximately 2%; the cumulative type II error rates spent at final analysis for platinum-sensitive cohort and platinum-refractory/resistant cohort are 9.9% and 9.4%, respectively.

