10.3. Statistical Analyses

Statistical analysis of this study will be the responsibility of Lilly or its designee.

All tests of treatment effects will be conducted at a 1-sided alpha level of 0.1, unless otherwise stated. Unless otherwise stated, all confidence intervals (CIs) will be given at a 2-sided 95% level.

Any change to the data analysis methods described in the protocol will require an amendment only if it changes a principal feature of the protocol. Any other change to the data analysis methods described in the protocol, and the justification for making the change, will be described in the SAP and the clinical study report. Additional exploratory analyses of the data will be conducted as deemed appropriate.

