5.1. General Considerations

Statistical analysis of this study will be the responsibility of Eli Lilly and Company. The interpretation of the study results will be the responsibility of the Lilly Clinical Research Physician/Clinical Research Scientist (CRP/CRS) and statistician. The CRP/CRS and statistician will also be responsible for the appropriate conduct of internal reviews for both the final study report and any study-related material to be authorized by Lilly for publication.

Any change to the data analysis methods described in the protocol will require an amendment ONLY if it changes a principal feature of the protocol. Any other change to the data analysis methods described in the protocol and the justification for making the change will be described in the clinical study report.

The study will enroll approximately 116 patients (58 platinum-sensitive patients, 58 platinum-refractory/resistant patients).

For the platinum-sensitive cohort, it is assumed that a true ORR of less than 20% indicates inadequate antitumor activity. Given that a futility interim analysis will be conducted on the first 29 patients' response data, then with a one-sided significance level of 0.1, a sample size of 58 patients will provide approximately 90% power to detect a true ORR of at least 35%.

For the platinum-refractory/resistant cohort, it is assumed that a true ORR of less than 5% indicates inadequate anti-tumor activity. Given that a futility interim analysis will be conducted on the first 29 patients' response data, then with a one-sided significance level of 0.1, a sample size of 58 patients will provide approximately 90% power to detect a true ORR of at least 15%.

The stopping rule for interim analysis and decision rule for final analysis are defined as follows:

- Platinum-sensitive cohort:
 - If 4 or fewer overall responses of confirmed CR or PR are observed in the first 29 patients, then the cohort will be terminated for futility; otherwise, the cohort will continue
 - If 16 or more overall responses of confirmed CR or PR are observed in all 58 patients, then the ORR is statistically significantly greater than 20%
- Platinum-refractory/resistant cohort:
 - If no overall response of confirmed CR or PR is observed in the first 29 patients, then the cohort will be terminated; otherwise, the cohort will continue
 - If 6 or more overall responses of confirmed CR or PR are observed in all 58 patients, then the ORR is statistically significantly greater than 5%

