5.10. Efficacy Analyses

5.10.1. Primary Outcome and Methodology

Best overall response (BOR) is defined as the best response recorded from the start of the study treatment until the end of treatment taking into account any requirement for confirmation, and will be derived based on investigator assessment of response and Response Evaluation Criteria in Solid Tumors (RECIST 1.1) (Eisenhauer et al. 2009).

Overall response rate is defined as the number of patients who achieve a BOR of CR or PR, divided by the total number of patients enrolled to the corresponding cohort (full analysis set). Complete or partial responses may be claimed only if the criteria for each are met at a subsequent time point (greater than 4 weeks). The ORR, with exact 95% and 80% CIs, will be summarized for each cohort using the Clopper-Pearson method.

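### The stated 9.4% type II error for the platinum-refractory/resistant cohort is not that of the stated rule (0/29, then 6/58), whose exact value is 11.7%

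*Protocol*

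**What the plan says.** Protocol 10.1 and SAP 5.1 carry the same error-rate text. They state that "the overall type II error rate, i.e. the probability of terminating an effective cohort, will be controlled using a Lan-DeMets spending function" of O'Brien-Fleming type. They add that "The type II error rate spent at interim analysis after the first 29 patients for each cohort is approximately 2" per cent and that "the cumulative type II error rates spent at final analysis for platinum-sensitive cohort and platinum-refractory/resistant cohort are 9.9% and 9.4%, respectively". On the design as a whole, Protocol 10.1 says that "with a one-sided significance level of 0.1, a sample size of 58 patients will provide approximately 90% power to detect a true ORR". In Cohort 1 the rate to be detected is 35% or more, against 20%. It makes the same claim for 15% against 5% in Cohort 2.

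The rules themselves are integer counts (Protocol 10.1 and 10.3.4, SAP 5.1):

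- **Cohort 1 (platinum-sensitive):** stop for futility at 4 or fewer responders in 29; succeed at 16 or more in 58.
- **Cohort 2 (platinum-refractory/resistant):** stop at 0 in 29; for success, SAP 5.1 reads "If 6 or more overall responses of confirmed CR or PR are observed in all 58 patients".

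For Cohort 1, SAP 5.1 adds that at 16 or more responders "then the ORR is statistically significantly greater than 20" per cent. Protocol 10.3 sets the level: "All tests of treatment effects will be conducted at a 1-sided alpha level of 0.1, unless otherwise stated". SAP 5.10.1 plans the interval estimates: "The ORR, with exact 95% and 80% CIs, will be summarized for each cohort using the Clopper-Pearson method".

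**The concern.** The error rates are printed to one decimal beside the integer rules and are glossed as a probability of terminating an effective cohort. A reader will take them as properties of those rules. A binomial count moves in whole steps, so a rule rounded from a continuous boundary need not keep the boundary's error rate. When the response rate is low, one responder is a large step. Neither document says that the percentages precede rounding, and neither gives exact operating characteristics.

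At stake is the stated chance of missing an active drug in the refractory/resistant cohort, a figure likely to be carried into the study report. A smaller matter is whether, in Cohort 1, the significance statement and the planned 80% interval agree at the threshold count.

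**Working it through.** **Inputs.** Null and target response rates p0 and p1 are 20% and 35% (Cohort 1) and 5% and 15% (Cohort 2). The one-sided level is 0.1. The looks are at 29 and 58 patients. The cut-offs are those listed above. All come from Protocol 10.1 and 10.3.4 and SAP 5.1.

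**Step 1: reproduce the stated figures.** The documents do not show their calculation, so this design is inferred. It uses a normal approximation with the null variance for the level and the alternative variance for power, a non-binding futility stop, and O'Brien-Fleming-type spending of β at information fraction 0.5.

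- Final boundary: c = 58·p0 + 1.2816·√[58·p0(1−p0)].
  - Cohort 1: 11.6 + 1.2816 × 3.046 = 15.50.
  - Cohort 2: 2.9 + 1.2816 × 1.660 = 5.03.
- Interim spend: b = 2[1 − Φ(z₁₋β/₂ / √0.5)], with interim boundary l = 29·p1 + Φ⁻¹(b)·√[29·p1(1−p1)].
  - Cohort 1: b = 1.97%, l = 10.15 − 2.059 × 2.569 = 4.86.
  - Cohort 2: b = 1.78%, l = 4.35 − 2.102 × 1.923 = 0.31.
- β is solved so that the total error under p1, from a bivariate normal with correlation √0.5, equals the β spent: **9.93%** (Cohort 1) and **9.38%** (Cohort 2).

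These match the stated 9.9%, 9.4% and about 2%. Moving each boundary up to the next whole responder gives the stated cuts: continue at 5 or more and succeed at 16 or more (Cohort 1); continue at 1 or more and succeed at 6 or more (Cohort 2). Using a single variance throughout does not fit. With the non-binding stop, Cohort 2 would be 22.0% (alternative variance) or 1.4% (null variance).

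**Step 2: exact error of the integer rules.** Let X1 and X2 be independent Binomial(29, p), r1 the stopping count and r the success count.

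P(success) = Σ over x1 > r1 of P(X1 = x1) × P(X2 ≥ r − x1); type II error = 1 − P(success) at p1.

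| | Cohort 1 | Cohort 2 |
|---|---|---|
| Interim stop at p1 | P(X1 ≤ 4) = 0.0101 | 0.85²⁹ = 0.0090 |
| Missed at the final analysis | 0.0836 | 0.1085 |
| **Cumulative type II error** | **0.0937** | **0.1174** |
| Stated | 9.9% | 9.4% |
| Power at p1 | 0.9063 | 0.8826 |
| Level at p0, stop binding | 0.1019 | 0.0685 |
| Level at p0, stop ignored | 0.1031 | 0.0691 |

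A simulation of 2,000,000 runs gave 9.39% and 11.76%.

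**Step 3: can another reading recover 9.4% in Cohort 2?** Ignoring the interim stop gives 11.51%. Success at 5 or more gives 5.6%. Neither does. The difference is 11.74 − 9.4 = 2.3 points. The order of the cohorts also reverses: the stated pair puts Cohort 2 below Cohort 1, while exactly it is above.

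**Step 4: the interval at the threshold count.** The exact 80% Clopper-Pearson interval at 16/58 is 19.91% to 36.49%, which includes 20%. At 6/58 it is 5.52% to 17.45%, which excludes 5%. The two-stage probability of ending on exactly 16/58 is 4.4% at a true rate of 20% and 5.5% at 35%.

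**The case against.** The strongest reply is that nothing was miscalculated. The text names a spending function and reports what it spends, and Step 1 returns those values. On this view a label is missing, not a number wrong. Power of roughly 90% holds for both cohorts. The 11.7% applies at exactly 15%, and the miss probability falls at higher response rates. Cohort 1's 9.9% and both interim figures overstate the risk. The rounding that costs power in Cohort 2 also lowers its false-positive rate to about 0.068. The thresholds are explicit and agree wherever they appear, so no decision would change. The 80% interval is descriptive and misses 20% by 0.09 points at a single count.

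All of this stands, and it limits the consequence. It does not make 9.4% a property of the rule with success at 6 or more. The documents themselves define the figure as a probability of terminating an effective cohort, and they do not mark the cumulative values as approximate. The 16/58 point is a side issue on which the main finding does not depend.

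**Conclusion.** The concern holds. For the rules as stated, exact cumulative type II error is 11.7% in Cohort 2 against 9.4% printed, and 9.4% in Cohort 1 against 9.9% printed. Only the Cohort 2 figure is too low, by 2.3 points, or about one quarter in relative terms (2.3 / 9.4). Cohort 1's exact level exceeds 0.1 by 0.2 to 0.3 points, which is negligible.

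The exact results assume independent patients with a common response rate and exactly 29 and 58 patients per cohort. Type II error and power are computed with the futility stop applied. The account of how 9.9% and 9.4% arose is an inference that fits closely; the exact values do not rely on it. This is an inaccuracy in the stated operating characteristics, not a flaw in the decision rules or the sample size.

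**What to change.** Keep every threshold and the sample size. In Protocol 10.1 and SAP 5.1:

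- Label about 2%, 9.9% and 9.4% as approximate spending-function design values before rounding to whole responders. The sponsor should confirm that this is how they were obtained.
- Add the exact values for the integer rules.
  - Cohort 1: interim type II error 1.0%, cumulative 9.4%, power 90.6%, one-sided level 0.102 (stop binding) to 0.103 (stop ignored).
  - Cohort 2: interim 0.9%, cumulative 11.7%, power 88.3%, level 0.068 to 0.069.

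In SAP 5.1 or 5.10.1, add one sentence: at exactly 16/58 the decision rule is met although the exact 80% interval (19.9% to 36.5%) just includes 20%, and the count is the decision criterion.

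The cost is wording and stated figures only, with no extra patients and no change to the design.
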